10.3. Samples for Biomarker Research

There is growing evidence that genetic variation may impact a patient's response to therapy. Variable response to therapy may be due to genetic determinants that impact drug absorption, distribution, metabolism, and excretion, the mechanism of action of the drug, the disease etiology and/or the molecular subtype of the disease being treated. Therefore, where local regulations and ERBs allow, a blood sample will be collected for pharmacogenetic analysis.

In the event of an unexpected AE or the observation of unusual response, the pharmacogenetic samples may be genotyped and analysis may be performed to evaluate a genetic association with response to the investigational product. These investigations may be limited to a focused candidate gene study or, if appropriate, genome wide analysis may be performed to identify regions of the genome associated with the variability observed in drug response. The pharmacogenetic samples will only be used for investigations related to disease and drug or class of drugs under study in the context of this clinical program. They will not be used for broad exploratory unspecified disease or population genetic analysis.

The samples will be coded with the subject number and stored for up to a maximum 15 years after the last subject visit for the study at a facility selected by the sponsor. The samples and any data generated from them can only be linked back to the subject by investigator site personnel. The duration allows the sponsor to respond to regulatory requests related to the investigational product.

Samples will be destroyed according to a process consistent with local regulation.

10.4. Safety Evaluations

Investigators are responsible for monitoring the safety of subjects who have entered this study and for alerting Lilly or its designee to any event that seems unusual, even if this event may be considered an unanticipated benefit to the subject.

The investigator is responsible for the appropriate medical care of subjects during the study. Planned safety assessments and measures are detailed in Section 10.4.5, but additional assessments and safety tests may be performed at the investigator's discretion.

The investigator remains responsible for following, through an appropriate health care option, AEs that are serious, considered related to study treatment or the study, or that caused the subject to discontinue before completing the study. The subject should be followed until the event is resolved or explained. Frequency of follow-up evaluation is left to the discretion of the investigator.

In addition to records of observations made at specific times, unexpected signs and symptoms and concomitant medications will be recorded in the clinical trial records throughout the study.

10.4.1. Safety Measures

At the end of the glucose clamp, the subject will receive a meal and undergo medical assessment before discharge. If glucose is still being infused at the time of clamp discontinuation, the subject will be monitored for safety. This may consist of hourly PG determinations and monitoring for continuing signs or symptoms of hypoglycemia. The subject will be observed until stable according to investigator judgment. Per investigator judgment, appropriate measures for symptomatic hypoglycemia and/or PG ≤ 70 mg/dL (≤ 3.9 mmol/L) will be applied. These measures may include oral glucose or glucose-containing food or drink, glucagon, or parenteral glucose, with follow-up testing, also according to investigator judgment.

10.4.2. Adverse Events

Lilly has standards for reporting AEs that are to be followed regardless of applicable regulatory requirements that may be less stringent.

Study site personnel will record the occurrence and nature of each subject's preexisting conditions, including clinically significant signs and symptoms of the disease under treatment in the study.

Cases of pregnancy that occur during maternal or paternal exposures to the investigational product and/or drug delivery system should be reported. Data on fetal outcome and breast-feeding are collected for regulatory reporting and drug safety evaluation.

After the informed consent form (ICF) is signed, site personnel will record any change in the condition(s) and the occurrence and nature of any AEs. All AEs related to protocol procedures are reported to Lilly or designee.

Any clinically significant findings from ECGs, labs, vital sign measurements, or other procedures, should be reported as an AE to Lilly or its designee.

In addition, all AEs occurring after the subject receives the first dose of the investigational product must be reported to Lilly or its designee via eCRF.

Investigators will be instructed to report to Lilly or its designee their assessment of the potential relatedness of each AE to protocol procedure, studied disease state, investigational product, and/or drug delivery system via eCRF.

The investigator will decide whether he or she interprets the observed AEs as either related to disease, to the study medication, study procedure, drug delivery system, or other concomitant treatment or pathologies. To assess the relationship of the AE to the investigational product, the following terminologies are defined:

- **Related:** a direct cause and effect relationship between the study treatment and the AE is likely.
- **Possibly related:** a cause and effect relationship between the study treatment and the AE has not been demonstrated at this time and is not probable, but is also not impossible.
- **Unrelated:** without question, the AE is definitely not associated with the study treatment.

As per Lilly's standard operating procedures, all "related" and "possibly related" AEs and SAEs will be defined as related to the investigational product.

If a subject's dosage is reduced or treatment is discontinued as a result of an AE, study site personnel must clearly report to Lilly or its designee via eCRF the circumstances and data leading to any such dosage reduction or discontinuation of treatment.

10.4.3. Serious Adverse Events

All episodes of hypoglycemia that are determined by the investigator to constitute severe hypoglycemia according to the definition in Section 10.4.4 should be reported as SAEs.

An SAE is any AE from this study that results in one of the following outcomes:

- death
- initial or prolonged inpatient hospitalization
- a life-threatening experience (that is, immediate risk of dying)
- persistent or significant disability/incapacity
- congenital anomaly/birth defect
- considered significant by the investigator for any other reason

Important medical events that may not result in death, be life-threatening, or require hospitalization may be considered SAEs when, based upon appropriate medical judgment, they may jeopardize the subject and may require medical or surgical intervention to prevent one of the outcomes listed in this definition.

When a condition related to the insulin pump necessitates medical or surgical intervention to preclude either permanent impairment of a body function or permanent damage to a body structure, the serious outcome of “required intervention” will be assigned.

Planned surgeries should not be reported as SAEs unless the underlying medical condition has worsened during the course of the study.

Study site personnel must alert Lilly or its designee of any SAE within 24 hours of investigator awareness of the event via a sponsor-approved method. If alerts are issued via telephone, they are to be immediately followed with official notification on study-specific SAE forms. This 24-hour notification requirement refers to the initial SAE information and all follow-up SAE information.

Serious adverse event collection begins after the subject has signed the ICF and has received investigational product. If a subject experiences an SAE after signing informed consent, but prior to receiving investigational product, the event will NOT be reported as serious unless the investigator feels the event may have been caused by a protocol procedure.

Serious adverse events occurring up to and including the subject’s last study visit will be collected, regardless of the investigator’s opinion of causation, in the clinical data collection database and the pharmacovigilance system at the sponsor.

The investigator does not need to actively monitor subjects for AEs once the trial has ended unless specified in the protocol. However, if an investigator becomes aware of SAEs occurring to a subject after the subject’s participation in the trial has ended, the investigator should report them to the sponsor, regardless of the investigator’s opinion of causation, and the SAEs will be entered in the pharmacovigilance system at the sponsor.

Information on SAEs expected in the study population independent of drug exposure and that will be assessed by the sponsor in aggregate periodically during the course of the trial may be found in the USPI.

10.4.3.1. Suspected Unexpected Serious Adverse Reactions

Suspected unexpected serious adverse reactions (SUSARs) are serious events that are not listed in the USPI and that the investigator identifies as related to investigational product or procedure. United States 21 CFR 312.32 and European Union Clinical Trial Directive 2001/20/EC and the associated detailed guidances or national regulatory requirements in participating countries require the reporting of SUSARs. Lilly has procedures that will be followed for the recording and expedited reporting of SUSARs that are consistent with global regulations and the associated detailed guidances.

10.4.4. Hypoglycemia

Subjects will be encouraged to perform SMPG whenever hypoglycemia may be suspected, either by symptoms experienced or perceived increased risk as related to dietary intake, physical activity, or inadvertent or atypical insulin dosing. All subjects will be instructed to treat an

SMPG ≤ 70 mg/dL (≤ 3.9 mmol/L) as hypoglycemia. All subjects will be advised to contact the study site if they experience severe hypoglycemia or SMPG < 50 mg/dL (< 2.8 mmol/L).

Hypoglycemic events should be appropriately recorded in the eCRF. The following hypoglycemia definition should be applied for reporting in the eCRF and evaluating hypoglycemic events;

Severe hypoglycemia: an event requiring assistance of another person to actively administer carbohydrate, glucagon, or other resuscitative actions. During these episodes, the subject has an altered mental status, and cannot assist in their care, is semiconscious or unconscious, or experienced coma with or without seizures, and may require parenteral therapy. Plasma glucose measurements may not be available during such an event, but neurological recovery attributable to the restoration of PG to normal is considered sufficient evidence that the event was induced by a low PG (≤ 70 mg/dL [≤ 3.9 mmol/L]).

Documented symptomatic hypoglycemia: an event during which typical symptoms of hypoglycemia are accompanied by a measured PG concentration ≤ 70 mg/dL (≤ 3.9 mmol/L).

Asymptomatic hypoglycemia: an event not accompanied by typical symptoms of hypoglycemia but with a measured PG concentration ≤ 70 mg/dL (≤ 3.9 mmol/L).

Nocturnal hypoglycemia: is defined as any documented symptomatic hypoglycemic event that occurs between bedtime and waking.

Hypoglycemic events recorded by the euglycemic clamp device during the evaluation will not be documented. In the case of a hypoglycemic event (other than severe), the actual PG value, if measured, should be recorded in the eCRF alongside one of the above terms, together with any treatments administered and should not be recorded as an AE. Cases of hypoglycemia may be treated with foods or beverages rich in carbohydrate such as fruit, juice, skimmed milk, or energy bars.

All episodes of hypoglycemia that are determined by the investigator to constitute severe hypoglycemia according to the definition provided should be reported as SAEs.

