Subjects should perform a 03:00 hours SMPG within 48 hours of any dose increase and should telephone the CRU the next morning if their 03:00 hours SMPG value is ≤70 mg/dL (≤3.9 mmol/L). The investigator may deviate from the algorithms, if deemed necessary, for the safety or well-being of the subject (for example due to illness, unusual SMPG patterns, or other safety concerns). Deviations from the algorithm should be discussed with Lilly, in advance if possible without compromising subject safety.

In the event of a subject reporting a severe hypoglycemic episode or any SMPG value is <50 mg/dL (<2.8 mmol/L), the investigator will make appropriate insulin adjustment per his/her judgment (this may be a 15% reduction in the appropriate U-500R mealtime dosage).

If a meal is skipped during the treatment period, the U-500R dose should be reduced by 50%.

Table IBHG.9.2. TID and BID Dosing Algorithms for U-500R Using Plasma-Equivalent Glucose Values

Algorithm	Insulin Dose to Adjust	Plasma-Equivalent Glucose Value	Value (mg/dL)	Action
TID Initial Dose Proportion 40:30:30	Pre-morning meal	Median pre-midday meal	≤70	Reduce dose by 10%
			71-130	No change in dose
			131-180	Increase dose by 5%
			181-220	Increase dose by 10%
			>220	Increase dose by 15%
	Pre-midday meal	Median pre-evening meal SMPG	≤70	Reduce dose by 10%
			71-130	No change in dose
			131-180	Increase dose by 5%
			181-220	Increase dose by 10%
			>220	Increase dose by 15%
BID Initial Dose Proportion 60:40	Pre-morning meal	Median pre-morning meal, median bedtime, or 03:00 hours SMPG	≤70	Reduce dose by 10%
			71-130	No change in dose
			131-180	Increase dose by 5%
			181-220	Increase dose by 10%
			>220	Increase dose by 15%
	Pre-evening meal	Median pre-morning meal, median bedtime, or 03:00 hours SMPG	≤70	Reduce dose by 10%
			71-130	No change in dose
			131-180	Increase dose by 5%
			181-220	Increase dose by 10%
			>220	Increase dose by 15%

Abbreviations: BID = twice daily; SMPG = self-monitored plasma glucose; TID = thrice daily.

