9.5.5 Blood Glucose Monitoring and Hypoglycemia

Hypoglycemic events will be appropriately recorded in the CRF.

In the case of a hypoglycemic event, the actual blood glucose value, if measured, will be recorded in the CRF, together with any treatments administered.

Hypoglycemic events will be listed, and summarised if appropriate. Severe hypoglycemic events will be reported as SAEs.

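### The nocturnal hypoglycemia term leaves out symptom-free 03:00 lows, overlaps another term under a one-term recording rule, and no term covers non-severe symptoms without a glucose value

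*Protocol*

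**What the plan says.** Protocol 10.4.4 gives four terms and says that they govern both eCRF reporting and evaluation of events.

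- *Severe*: the subject needs another person's help. This is the only term that can be met without a glucose value: "Plasma glucose measurements may not be available during such an event".
- *Documented symptomatic*: "an event during which typical symptoms of hypoglycemia are accompanied by a measured PG concentration" of 70 mg/dL or below.
- *Asymptomatic*: "an event not accompanied by typical symptoms of hypoglycemia but with a measured PG concentration" of 70 mg/dL or below, at any time of day.
- *Nocturnal*: "Nocturnal hypoglycemia: is defined as any documented symptomatic hypoglycemic event that occurs between bedtime and waking".

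For any event other than severe, the recording rule is that "the actual PG value, if measured, should be recorded in the eCRF alongside one of the above terms". The same rule keeps such events off the adverse event page. Self-measurement when hypoglycemia is suspected is encouraged, not required.

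Night readings are scheduled in Protocol 9.4: "Subjects should perform a 03:00 hours SMPG within 48 hours of any dose increase and should telephone the CRU the next morning" if the value is 70 mg/dL or below. Section 7.1.4 repeats the 03:00 check, and Attachment 3 allows for up to 8 such readings.

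SAP 9.5.5 defines no classes and no nocturnal attribute. It says: "Hypoglycemic events will be listed, and summarised if appropriate". SAP 9.5.7 plans no safety inference.

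**The concern.** A 03:00 reading is taken because a dose was raised, whether or not the subject feels anything. If it is low and the subject has no symptoms, the protocol responds to it, but its own nocturnal term cannot hold it. The class whose name suggests night-time lows therefore leaves out a kind of low that the night check is designed to find.

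Two further gaps sit in the same section. Nocturnal is a subset of documented symptomatic, so a coder allowed one term must choose between two that both fit. And a symptomatic event that was treated but not measured fits none of the non-severe terms, while the adverse event page is closed to it.

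At stake is how readable the safety description is. Part B is self-administered at home with dose titration. Protocol 5.1 describes activity lasting up to 24 hours after a single dose, and a predicted basal effect with both BID and TID dosing. Night lows are a foreseeable question there, and the classes as written would answer it partly according to the coder's choice.

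**Working it through.** The plan states no hypoglycemia rate, so there is no figure to reproduce. The check sets each kind of night event against the four definitions and the one-term rule.

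**Step 1. Night events against the terms in Protocol 10.4.4**

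| Night event | Terms met | Classed nocturnal? | In the total? |
|---|---|---|---|
| Non-severe, symptoms, PG 70 mg/dL or below | Documented symptomatic and nocturnal | Only if the coder picks that term | Yes |
| Non-severe, no symptoms, PG 70 mg/dL or below | Asymptomatic | No | Yes |
| Non-severe, symptoms, no PG measured | None | No | Only if the site records it without a fitting term |
| Severe, no PG measured | Severe | No | Yes, and as an SAE |
| Severe, typical symptoms, PG 70 mg/dL or below | Severe; also fits the wording of documented symptomatic | Possible | Yes, and as an SAE |

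Rows 2 and 4 fall outside nocturnal by definition. Row 1 depends on coding. Row 3 has no home.

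**Step 2. The protocol's own titration examples (9.4.1 and 9.4.2)**

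Readings of 70 mg/dL or below:

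- TID Example 2: 68 (bedtime), 60 (03:00)
- TID Example 3: 66, 68, 64
- BID Example 2: 58
- BID Example 3: 66, 66, 70, and 70 (03:00)
- TID Example 1 and BID Example 1: none

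Total: 2 + 3 + 1 + 4 = 10, of which 2 are at 03:00. In both of those examples the 03:00 value leads to a 10% reduction of the evening dose. All 10 readings fit a class and enter the total whether or not there were symptoms. The two night readings give anywhere from 0 to 2 nocturnal events, depending on symptoms, which the examples do not state, and on the term chosen.

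**Step 3. How far the nocturnal class could fall short (assumed shares)**

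Let *a* be the share of non-severe night events without symptoms, and *u* the share with symptoms but no PG. Neither is in the documents. I assume *a* from 0% to 75% and *u* from 0% to 20%.

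- Largest share that can be classed nocturnal = 1 − *a* − *u*. At *a* = 0 and *u* = 0 this is 100%. At *a* = 0.50 and *u* = 0.10 it is 1 − 0.50 − 0.10 = 40%. At *a* = 0.75 and *u* = 0.20 it is 1 − 0.75 − 0.20 = 5%.
- If coders always choose documented symptomatic for row 1, the share is 0% whatever *a* and *u* are.
- Share of these events kept in the total = 100% if unmeasured events are recorded, and 1 − *u* if they are dropped, that is 80% to 100%.

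The width of the first range shows that the shortfall cannot be sized from the plan. The last line shows that the total is at risk only through row 3.

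**The case against.** The strongest reply is that this is labelling with little consequence. Restricting nocturnal to documented symptomatic events is an explicit choice. A symptom-free 03:00 low is still recorded as asymptomatic with its value. The subject telephones the unit, and titration uses the reading whatever term is on the eCRF. SAP 9.4.2 plans SMPG listings and 3am profiles as appropriate, SAP 9.1 lists all databased data, and SAP 9.5.1 tabulates serious events. Hypoglycemia is in no study objective. The eCRF and the table shells are not available here and may already carry event times.

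Much of that stands, and it limits the point in four ways.

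- A reader might infer that total hypoglycemia is undercounted. The documents do not support this. The nocturnal restriction and the overlap relabel events without removing them. Only symptoms without a PG could drop out, and the text asks for events to be recorded with the PG value only where one was measured, so their loss is possible but not certain.
- A reader might infer that no severe night event can be nocturnal. That holds only where no PG was measured. With typical symptoms and a PG of 70 mg/dL or below, the event fits the wording.
- A reader might infer biased nocturnal rates for TID against BID. The plan contains no such rates.
- The overlap does not always lose information. If the narrower term is used, the documented symptomatic count is recovered by adding the two codes. Night timing is lost from the class only when the broader term is chosen.

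What the reply does not remove is that the section says its definitions govern evaluation as well as recording. It gives no precedence between overlapping terms, and it foresees an event without a PG value for which it offers no term. The SAP does not fill either gap.

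**Conclusion.** The concern holds as a defect in classification. Followed as written, symptom-free 03:00 lows and severe night events without a PG are not classed as nocturnal, symptomatic night lows can be coded in two ways, and non-severe symptomatic events without a PG may be lost or coded inconsistently.

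The direction for the nocturnal class follows from the definitions alone. The size does not: the 5% to 100% ceiling above rests entirely on assumed shares. The total count is not shown to be wrong. The definitions cover the whole study, and Part B is the main setting because the home titration and the 03:00 checks are there. The outputs are descriptive, so no endpoint or inference is affected. The change is worth making because it is cheap and the classes describe safety.

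**What to change.** In Protocol 10.4.4, take nocturnal out of the list of alternative terms and record it as a separate yes/no attribute (onset between bedtime and waking) for every class, including severe and asymptomatic. State that a low found on waking for the 03:00 reading counts as yes. Add a class for typical symptoms with no PG measured, recorded on the same hypoglycemia page.

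In SAP 9.5.5, name the classes, list every event with its class and nocturnal flag, and, if events are summarised, tabulate events and subjects by class and flag for each treatment.

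The cost is definition wording, one added flag and one added code on the eCRF, and the matching listing or table. Reported nocturnal counts will be higher than under the present term. No measurement is added, and no glucose threshold, dose or management rule changes.

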10.4.5. Other Safety Measures

10.4.5.1. Physical Examination

Physical examinations and routine medical assessments will be conducted as specified in the Study Schedule and as clinically indicated ([Attachment 1](#)).

10.4.5.2. Vital Signs

Blood pressure and pulse rate will be measured as specified in the Study Schedule and as clinically indicated ([Attachment 1](#)).

Blood pressure and pulse rate should be measured after the subject has been supine for at least 5 minutes.

If orthostatic measurements are required, subjects should be supine for at least 5 minutes and stand for at least 3 minutes.

If the subject feels unable to stand, supine vital signs only will be recorded.

Unscheduled orthostatic vital signs should be assessed, if possible, during any AE of dizziness or posture-induced symptoms. Additional vital signs may be measured during each study period if warranted and agreed upon between the sponsor and investigator.

